18.0 Confidentiality

A. Confidentiality of Study Data

*Describe the local procedures for maintenance of confidentiality of **study data and any records that will be reviewed for data collection**.*

18.1 A. Where and how will all data and records be stored? Include information about: password protection, encryption, physical controls, authorization of access, and separation of identifiers and data, as applicable. Include physical (e.g. paper) and electronic files.

Response:

All data records will be stored on password protected computers and or in locked cabinets within the research department. These files will only be accessible by authorized study personnel.

Each subject will be assigned a randomization number (1 to 20) depending on the sequence of their visit, and each subject will also be assigned a stimulation code which decides whether he/she will receive active or sham stimulation. This stimulation code is determined at the time of randomization. After that, we will only retain the subject's initials, randomization number, and a stimulation code. These identifiers will not be separated from the data.

The data recorded on the paper forms will be transferred to Excel file and will be verified by another staff member at the research center.

18.2 A. How long will the data be stored?

Response: Data and specimens storage has no expiration date and will be stored for a minimum of 7 years. The researchers may continue to rely on this for future use in research study

B. Who will have access to the data?

Response:

Those physicians, nurses, and laboratory staff that are on all documentation for the study will have access to the data and specimens

18.3 A. Who is responsible for receipt or transmission of the data?

Response: Those physicians, nurses, and laboratory staff that are on all documentation for the study will have access to the data and specimens and can handle transfer of data and samples

18.4 A. How will the data be transported?

Response:

All data are stored at one location and is not transported unless it is being archived. At that point files will be transferred to Iron Mountain for storage and archiving. Samples that are transported will be done so using dry ice in a properly labeled Styrofoam container by the laboratory technician.

B. Confidentiality of Study Specimens

Describe the local procedures for maintenance of confidentiality of study specimens.

N/A: No specimens will be collected or analyzed in this research.
(Skip to Section 19.0)

18.5 B. Where and how will all specimens be stored? Include information about: physical controls, authorization of access, and labeling of specimens, as applicable.

Response: The data and specimens will be stored in the laboratory located at [name] and at the CTRC located in [name]. Samples will be stored in a locked -80° C freezer.

18.6 B. How long will the specimens be stored?

Response: Data and specimens storage has no expiration date and will be stored for a minimum of 7 years. The researchers may continue to rely on this for future use in research study

18.7 B. Who will have access to the specimens?

Response: Those physicians, nurses, and laboratory staff that are on all documentation for the study will have access to the data and specimens

18.8 B. Who is responsible for receipt or transmission of the specimens?

Response: Those physicians, nurses, and laboratory staff that are on all documentation for the study will have access to the data and specimens and can handle transfer of data and samples

18.9 B. How will the specimens be transported?

Response: Samples that are transported will be done so using dry ice in a properly labeled Styrofoam container by the laboratory technician

19.0 Provisions to Monitor the Data to Ensure the Safety of Subjects

- N/A:** This study is not enrolling subjects, or is limited to records review procedures only. This section does not apply.

NOTE: Minimal risk studies may be required to monitor subject safety if the research procedures include procedures that present unique risks to subjects that require monitoring. Some examples include: exercising to exertion, or instruments that elicit suicidality or substance abuse behavior. In such cases, N/A is not an acceptable response.

19.1 Describe the plan to periodically evaluate the data collected regarding both harms and benefits to determine whether subjects remain safe.

Response:

According to previous studies, active tDCS was associated with a higher prevalence of skin redness compared with control group. Other possible adverse reaction reported in the past include scalp burning, tingling, sleepiness, difficulty with concentrating, headache, neck pain and scalp pain, but the prevalence of these reactions was not found to be different from control group. These side effects are generally transient and resolve with time without active intervention. Contraindications for the use of tDCS include underlying psychiatric illness, personal or family history of seizures, underlying skin disorders, history of implanted pacemaker, medication pump, vagal stimulator, deep brain stimulator, TENS unit, ventriculoperitoneal shunt or any metallic implant on the head. Although not a direct contraindication, scarring within the brain may modify the effects of the tDCS and therefore prior neurosurgical procedures or radiation treatment to the brain are also considered contraindications. Subjects with any of these known medical conditions will be excluded. Immediately before and after tDCS administration, we will systematically monitor the presence of adverse events using a standard tDCS safety questionnaire that has been previously published (Brunoni et al., 2011). Subjects who report significant side effects related to the tDCS may also be excluded based on the investigator's judgement.

Continuous glucose monitor use is occasionally associated with insertion site discomfort or skin irritability. The effect is generally mild and resolve without intervention. We will demonstrate the correct way of using continuous glucose monitor to subjects to minimize the side effects. We will also ask them if they experience any side effects on the visit after continuous glucose monitor use and they are encouraged to report side effects over telephone.

The principal investigator [name], PhD and co-investigators [name] [name] and [name] will review the data of adverse reaction every 3 months to assess the safety and potential benefits to the participant. Furthermore, they will also assess other risks including the physical, psychological, social, legal and economic harm to these patients. The investigators listed above will carefully watch for any invasion of privacy and breach of confidentiality.

19.2 Describe what data are reviewed, including safety data, untoward events, and efficacy data.

Response:

Height, Weight, and adverse reaction reported by subjects are monitored every visit to ensure safety.

19.3 Describe any safety endpoints.

Response:

Adverse event (AE): Any untoward or unfavorable medical occurrence in a human subject, including any abnormal sign (for example, abnormal physical exam or laboratory finding), symptom, or disease, temporally associated with the subject's participation in the research, whether or not considered related to the subject's participation in the research

Serious adverse event (SAE): Any adverse event temporally associated with the subject's participation in research that meets any of the following criteria: 1) results in death;

2) is life-threatening (places the subject at immediate risk of death from the event as it occurred); 3) requires inpatient hospitalization or prolongation of existing hospitalization; 4) results in a persistent or significant disability/incapacity; 5) results in a congenital anomaly/birth defect; or any other adverse event that, based upon appropriate medical judgment, may jeopardize the subject's health and may require medical or surgical intervention to prevent one of the other outcomes listed in this definition (examples of such events include allergic bronchospasm requiring intensive treatment in the emergency room or at home, blood dyscrasias or convulsions that do not result in inpatient hospitalization, or the development of drug dependency or drug abuse)

The following table represents the time frames for reporting serious events at the State University of New York at Buffalo:

TIMEFRAMES FOR REPORTING ON-SITE “SERIOUS” EVENTS/PROBLEMS (SEPs)	
Type of Report	When to Report
Deaths - except when death is the endpoint of the study	Within 24-hours of knowledge or notification
Life-threatening (i.e., events/problems that place the subject at immediate risk of death from the event as it occurred)	Within 72-hours of knowledge or notification
Required hospitalization or prolongation of existing hospitalization	Within 72-hours of knowledge or notification
Resulted in persistent or significant disability or incapacity	Within 72-hours of knowledge or notification
Resulted in congenital anomaly or birth defect	Within 72-hours of knowledge or notification

Based on appropriate clinical judgment, the event required or may require medical or surgical intervention to:
 
 • prevent a life-threatening event/problem (the subject is at immediate risk of death from the event as it occurred) • Required hospitalization or prolongation of existing hospitalization • Resulted in persistent or significant disability or incapacity • Resulted in congenital anomaly or birth defect 	
Within 72-hours of knowledge or notification

Deviation, in an emergency situation, from the approved investigational plan initiated in order to protect the life or physical well-being of a subject
	
Within 5 days of the emergency

Deviation, in an emergency situation, from the approved investigational plan initiated in order to eliminate an apparent hazard to a participant
	
Within 5 days of the emergency

Increased Risk of Harm to subjects or others than was previously known or recognized (whether or not actual harm has occurred). Risks may be physical, psychological, economic, or social:
	
Within 10 working days of knowledge or notification

Examples:
 
 • Theft or loss of stored research data • A subject complaint indicates unexpected risks • Unexpected subject withdrawal poses increased risks to the subject or others • Incarceration of an enrolled subject, in a study not approved for participation of prisoners, where ceasing all study involvements or interventions with the now-incarcerated prisoner-subject may increase risks to his/her health or safety. 	

Breach of Confidentiality that caused harm or places subjects or others at increased risk of harm (physical, psychological, economic, or social harm (even if actual harm has not occurred).
	
Within 10 working days of knowledge or notification

Significant impact on the integrity of the research data
 
Examples:
 
 • Unplanned destruction of study records • Withdrawal of subject(s) impacts data integrity or causes inability to complete the study 	
Within 10 working days of knowledge or notification

Unanticipated Adverse Device Effects
 
Any serious adverse effect on health or safety of any life-threatening problem or death caused by, or associated with, an FDA regulated device, if that effect problem or death was not previously identified in nature, severity, or degree of incidence in the investigational plan or application, or any other unanticipated serious problem associated with a device that relates to the rights, safety, or welfare of subjects.
	
Within 10 working days of knowledge or notification

Any event/problem that would cause the sponsor to modify the investigator's brochure, informed consent document or would prompt other action by the IRB to assure protection of subjects.	Within 10 working days of knowledge or notification.
Any other “Serious” Event/Problem not described above	Within 10 working days of knowledge or notification

19.4 Describe how the safety information will be collected (e.g., with case report forms, at study visits, by telephone calls with participants).

Response:

On site during the visit. We also encourage participants to call us if they develop any adverse reaction

19.5 Describe the frequency of safety data collection.

Response:

The data collection will be done at all study visits. The patients, however, will be asked to report any adverse event or safety related information via phone as soon as it occurs.

19.6 Describe who will review the safety data.

Response: The safety data will be reviewed by the principle and sub investigators as well as the research coordinator.

19.7 Describe the frequency or periodicity of review of cumulative safety data.

Response: Safety data will be reviewed every three months during the duration of the study. Study endpoint data will be reviewed once after half of the recruited patients have completed the study and then at the end of the study.

19.8 Describe the statistical tests for analyzing the safety data to determine whether harm is occurring.

Response: We will calculate the percentage of participants that developed any adverse reaction during the course of the study. We will use Fisher exact test to compare the percentage of participants that developed serious adverse reaction (which leads to withdrawal of subject) between group with active tDCS and sham tDCS. We will use two sample exact test for incidence rate data to compare the incidence of mild adverse reaction (which did not lead to withdrawal of subjects) between the two groups.

19.9 Describe any conditions that trigger an immediate suspension of the research.

Response: Inability to tolerate the tDCS administration, continuous glucose monitor or blood draw

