Subjects will come back within 2 weeks and will arrive after having fasted overnight (10 hours) at 7 to 7:30 am. They will then be randomized to either active tDCS or sham tDCS with block randomization (block size of 10). We will test urine pregnancy test to rule out pregnancy. Pregnant subject will be excluded from the study. We will also administer the three-factor eating questionnaire (Stunkard and Messick, 1985), which measures eating habits and attitudes toward food, weight and dieting, and a personality questionnaire, the Big Five (Costa and McCrae, 1989). We will evaluate cognitive responses to food with a 20-minute computerized task designed to engage the inhibitory control circuit when confronted with food stimuli, as well as engaging the other two components of executive function: working memory and cognitive flexibility. The task consists of 3 parts: a version of a Go/No-Go (GNG) task modified for food; an N-back memory task with food images, similar to a task used in a previous study; and a combined N-back and GNG task. In the food modified GNG task subjects have to press the space bar of a computer in response to pictures of low-calorie food, refraining from pressing when the pictures are of high-calorie food (25% of the time). In the N-back task, subjects will press the space bar when the picture displayed matches the picture displayed two images before. In the combined task, the subject will press the space bar when a picture of low-calorie food matches the picture displayed two images before, while refraining from pressing when a high-calorie food matches the picture displayed two images before.

Blood sample for BDNF and COMT gene test will be collected. We will also collect blood sample for plasma insulin and glucose level. We will download data from the continuous glucose monitor.

Subjects assigned to active tDCS group will receive 30 min of anodal tDCS delivered with a neuroConnVR DCSTIMULATOR device (neuroConn GmbH, Ilmenau, Germany), at a constant current of 2 mA (with a 30-second ramp at on- and offset) using two sponge electrodes soaked in a sterile 0.9% sodium chloride solution. The anode electrode will be placed over F3 (10–20 EEG system), with the cathode electrode placed over the contralateral supraorbital area, above the right eyebrow. This montage was used in a recent study that showed reduction of body weight and intake of soda and fat in a sample of obese subjects.

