Subjects assigned to sham tDCS group will receive 15 seconds of anodal tDCS delivered with a neuroConnVR DCSTIMULATOR device (neuroConn GmbH, Ilmenau, Germany), at a constant current of 2 mA (with a 30-second ramp at on- and offset) using two sponge electrodes soaked in a sterile 0.9% sodium chloride solution. However, they will stay at the research center for 30 minutes with electrodes on their scalp. Before starting the stimulation, a code will need to be entered into the tDCS machine which will decide whether a sham or active stimulation will be performed by the machine automatically in the next 30 minutes. At the beginning of the study, a code that is associated with either active stimulation or sham stimulation will be assigned to the subject based on the randomization. However, neither the subject or the operator of tDCS machine will know what does the code represent.

Visit 2: Subjects will come back next day to receive the second session of the same intervention.

Visit 3: Subjects will come back next day to receive the third session of the same intervention.

Visit 4: Subjects will come back next day to receive the fourth session of the same intervention.

Visit 5: Subjects will fast overnight (10 hours) and come back next morning at 7 to 7:30 AM to receive the fifth session of the same intervention. We will then measure body mass index, plasma insulin and glucose, appetite and cognitive function in response to food. Continuous glucose monitor will be reinstalled, and subjects will be instructed to wear it and document the time and types of food of every meal for at least 72 hours after this visit and 72 hours before the next visit. Subject will be instructed on how to insert and remove continuous glucose monitor again.

Visit 6: Subjects will fast overnight (10 hours) and come back next morning at 7 to 7:30 AM in 4 weeks after visit 5. We will measure body mass index, plasma insulin and glucose, appetite and cognitive function in response to food again. We will download data from the continuous glucose monitor. We will also ask if the subject believed that he/she received active or sham tDCS.

10.2 Describe what data will be collected.

NOTE: For studies with multiple data collection points or long-term follow up, consider the addition of a schedule or table in your response.

Response:

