20.0 Withdrawal of Subjects

N/A: This study is not enrolling subjects. This section does not apply.

20.1 *Describe anticipated circumstances under which subjects may be withdrawn from the research without their consent.*

Response: Inability to tolerate the tDCS administration, continuous glucose monitor or blood draw. The principal investigator of the study can remove a participant from the research study without their approval if for any reason he/she feels is appropriate, including: severe side effect, injury or medical condition which may place subjects at risk of further complications if he/she continues to participate, failure to keep scheduled appointments, or other administrative reasons.

If any of the subjects become pregnant during the period of study, he/she will need to withdraw from the study.

20.2 *Describe any procedures for orderly termination.*

NOTE: Examples may include return of study drug, exit interview with clinician. Include whether additional follow up is recommended for safety reasons for physical or emotional health.

Response:

We will recommend that the subject come back for an exit visit to make sure he/she is not experiencing side effect from tDCS. However, they can also follow up with us in the clinic since the subjects are recruited from our clinic patients. They will also be asked to return the continuous glucose monitor after the study.

20.3 *Describe procedures that will be followed when subjects withdraw from the research, including retention of already collected data, and partial withdrawal from procedures with continued data collection, as applicable.*

Response: If a subject withdraws from the research, the data collected to that point will be used toward the research finding.

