Contraindications for the use of tDCS include underlying psychiatric illness, personal or family history of seizures, underlying skin disorders, history of implanted pacemaker, medication pump, vagal stimulator, deep brain stimulator, TENS unit, ventriculoperitoneal shunt or any metallic implant on the head. Although not a direct contraindication, scarring within the brain may modify the effects of the tDCS and therefore prior neurosurgical procedures or radiation treatment to the brain are also considered contraindications. Subjects with any of these known medical conditions will be excluded. Immediately before and after tDCS administration and on the last visit of the study, we will systematically monitor the presence of adverse events using a standard tDCS safety questionnaire that has been previously published (Brunoni et al., 2011). Subjects who report significant side effects related to the tDCS may also be excluded based on the investigator's judgement.

Continuous glucose monitor use is occasionally associated with insertion site discomfort or skin irritability. The effect is generally mild and resolve without intervention. We will demonstrate the correct way of using continuous glucose monitor to subjects to minimize the side effects. We will also ask them if they experience any side effects on the visit after continuous glucose monitor use. We will discontinue the use of it on a subject if he/she is not able to tolerate it.

In order to lessen the risk of breach of confidentiality, subjects will be allowed to address their question and concerns in private with the research coordinator, study nurse and/or research physician. At any time during the study the patient is able to place privacy

restriction to their protected health information (i.e. telephone message, PHI release forms) which the study personnel document and respect. All data records will be stored on password protected computers and or in locked cabinets within the research department. These files will only be accessible by authorized study personnel

21.3 If applicable, indicate which procedures may have risks to the subjects that are currently unforeseeable.

Response: tDCS. There is no long term study on the safety of tDCS. As a result, the long term risk of this procedure is currently unforeseeable.

21.4 If applicable, indicate which research procedures may have risks to an embryo or fetus should the subject be or become pregnant.

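### Removal for tDCS side effects or intolerance after randomisation can lose the Visit 5 and Visit 6 weights, because the withdrawal rules do not carry through Aim 1's promise of a one-month weight for every participant

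*Combined protocol and SAP*

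**What the plan says.** The primary endpoint is change in weight as a percentage of baseline (Section 2.1). Aim 1 (Section 1.1) promises a weight for every participant at the start and one month after the last session. Section 10.1 places the later weight at Visit 6, four weeks after Visit 5.

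Randomisation is at Visit 1, before any stimulation: "They will then be randomized to either active tDCS or sham tDCS with block randomization (block size of 10"). Sessions run on consecutive days from Visit 1 to Visit 5. At Visit 5 the fifth session comes first: "We will then measure body mass index, plasma insulin and glucose, appetite and cognitive function in response to food".

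Three sections allow removal after that point for reasons tied to tDCS:

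- Section 19.1, repeated in 21.2: "Subjects who report significant side effects related to the tDCS may also be excluded", at the investigator's judgement.
- Section 20.1, on withdrawal from the research without the subject's consent: "Inability to tolerate the tDCS administration, continuous glucose monitor or blood draw. The principal investigator of the study can remove a participant", with severe side effects among the listed grounds.

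On what follows removal, Section 20.2 says "We will recommend that the subject come back for an exit visit to make sure he/she is not experiencing side effect from tDCS" and mentions ordinary clinic follow-up as an alternative. The prompt for Section 20.3 asks about "partial withdrawal from procedures with continued data collection, as applicable". The whole response is: "If a subject withdraws from the research, the data collected to that point will be used toward the research finding".

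**The concern.** The rules do not separate stopping stimulation from leaving the study. A subject who cannot tolerate the current can usually still step on a scale four weeks later, yet the only stated consequence of removal is that existing data are kept.

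The timing makes this matter more. Removal for a reaction to tDCS will mostly fall before the Visit 5 weight, so the subject has no value at either post-baseline time in the Section 17.1 model (Visit 5 and Visit 6). The loss comes after randomisation and for a treatment-related reason. If it fell unevenly between arms, and the removed subjects differed in weight change, the comparison would shift. Even if it fell evenly, precision would suffer in a trial of 20.

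The plan itself foresees such removals: Section 19.8 identifies a serious adverse reaction by withdrawal of the subject and tests its frequency between arms.

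**Working it through.** The documents give no removal rate, SD, effect size, alpha or power, so there is no figure to reproduce. The check has two parts.

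**1. Does any passage secure the Visit 6 weight for a removed subject?**

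- Aim 1 states the commitment, but Sections 20.1 to 20.3 give no step that carries it out after removal.
- The exit visit in 20.2 is only recommended, is for side effects, and names neither a weight nor a four-week time. Clinic follow-up has no study measurement attached.
- Section 19.2 has weight monitored at every visit. This covers attended visits only, and between Visits 1 and 5 those fall within days of randomisation, not at one month.
- Medical records are a data source (Section 10.3), with no timing.
- Section 17.1 names a sensitivity analysis for missing data without a method. It would handle a gap, not prevent one.

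None of these secures it.

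**2. How large could the effect be?**

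Inputs: 20 subjects (Section 5.1). Ten per arm is an assumption, since 1:1 allocation is not stated. The losses (1 to 3 active, no sham) and the gap in weight change between removed and remaining subjects (0.5 to 1 SD) are illustrations only.

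Shift = (active lost/10 − sham lost/10) × gap.

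- Smallest case: 0.1 × 0.5 = 0.05 SD.
- Largest case: 0.3 × 1.0 = 0.30 SD.
- Equal losses of similar subjects: 0.

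The sign depends on whether removed subjects would have lost more or less weight than the rest.

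Standard error of the difference = √(1/nA + 1/nS), in SD units:

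| Active v sham with Visit 6 weight | SE | Change |
|---|---|---|
| 10 v 10 | 0.447 | – |
| 9 v 10 | 0.459 | +3% |
| 8 v 10 | 0.474 | +6% |
| 7 v 10 | 0.493 | +10% |
| 7 v 7 | 0.535 | +20% |

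Every shift considered is below 0.447 SD.

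**Does the mixed model repair it?** A simulation used the three planned times and an arm-by-time normal model. It assumed a baseline SD of 20 kg, change SDs of 1 kg (Visit 5) and 2 kg (Visit 6), correlation 0.5, and baseline only for lost subjects, with 20,000 trials per case. Shifts were 0.05 and 0.10 SD for one active loss (gap 0.5 and 1 SD), 0.10 and 0.20 for two, 0.15 and 0.30 for three, and 0.00 for three lost from each arm. These match the simple formula. This is expected: a subject with no post-baseline weight tells the model nothing about the gap. The simulation uses one set of SDs, works in kg rather than percent, and leaves out weights from attended early visits, so it only confirms the formula.

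**The case against.** The case against has real force. Aim 1 is anchored to the last session, not to completing five, so it can be applied to a subject who stops early. The rule in 19.1 and 21.2 is permissive and does not say what the subject is excluded from: stimulation, follow-up or analysis. Section 20.3 does not forbid later weighing. Removals may be rare: sessions are 30 minutes at 2 mA, Section 19.1 calls the effects generally transient, and Section 31.3 reports no major adverse effects in schemes of up to 10 consecutive days. The illustrated shifts are modest beside the imprecision of a declared pilot.

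Most of this stands and limits the point. Three stronger readings that a reader might infer are not supported:

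- That the plan forbids weighing removed subjects or drops them from analysis. It says neither, and 20.3 keeps the data already collected.
- That the plan ignores one-month follow-up altogether. Aim 1 is a stated commitment; the fault is that the withdrawal rules do not carry it out.
- That differential loss, or a bias in a known direction, is established. Section 19.1 reports an arm difference only for skin redness and none for the other reactions.

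What does not stand is that this is only missing detail. Section 20.1 concerns withdrawal from the research, so the ambiguity in 19.1 does not rescue it, and 20.3 was asked about continued data collection and gave none. The plan can draw the distinction when it chooses: for the glucose monitor, Section 21.2 says "We will discontinue the use of it on a subject if he/she is not able to tolerate it".

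**Conclusion.** The point holds in a limited form. Sections 19.1, 20.1, 20.3 and 21.2, followed as written, can cost the Visit 5 and Visit 6 weights of a randomised subject who could still be weighed, and no other section secures them. It should be corrected because the correction is cheap, not because the damage is shown to be large.

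The size rests on assumptions: 10 per arm, 1 to 3 active subjects lost before Visit 5, none from sham, and a gap of 0.5 to 1 SD. On these the shift is 0.05 to 0.30 SD in either direction, under one standard error, and the standard error rises by 3% to 10%. The real frequency, arm difference and direction are unknown. Confidence is medium.

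**What to change.** - **Sections 19.1, 20.1 and 21.2:** state that side effects of tDCS, or inability to tolerate it, including severe ones, stop stimulation only, unless continued attendance is itself unsafe or the subject withdraws consent. Naming severe reactions avoids a clash with the severe side effect ground in 20.1.
- **Section 20.3:** state that such subjects are asked to attend Visits 5 and 6 for at least weight and are analysed in their randomised arm.
- **Section 19.8:** identify a serious reaction as one that led to stopping tDCS or to withdrawal, and a mild one as one that led to neither. Otherwise subjects who stop stimulation but stay in the study would move out of the serious category.

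The wording on glucose monitor and blood-draw intolerance, on pregnancy, and in Section 19.9 is outside this point and can be left alone.

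**Cost:** edits to five sections, plus up to two already scheduled visits per affected subject. Section 25.1 gives 50 dollars per visit and 10 dollars for parking. Reading parking as per visit, 2 × 60 = 120 dollars per subject, or 120 to 360 dollars for 1 to 3 subjects.

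**Downside:** partly treated subjects dilute the effect. If 1 to 3 of 10 active subjects gain none of it, the dilution is 1/10 to 3/10, at most 10% to 30%. That is the usual price of analysing subjects as randomised.
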